8.6 Vital Signs

For vital signs, the observed values and changes from baseline will be summarized by collected time points. Change from baseline will be calculated as (value at a treatment cycle – value at baseline). Frequencies and percentage of values meeting PCS criteria ([Table 5](#)) at any time post-baseline will be presented. The denominator for percentages will be the number of subjects who have a value at baseline and post-baseline.

Tables summarizing observed values and changes from baseline will be completed for the study cohorts. The number (%) of subjects with values that satisfy PCS criteria at any time during treatment will be provided for the study cohort and the integrated treatment group. PCS High criteria for BP are consistent with specific levels included in CTCAE criteria for Grade 1, 2, and 3 hypertension.

All vital sign data will be included in a by-subject data listing.

Table 5: Potentially Clinically Significant Post-Baseline Vital Signs

Vital Sign	Unit	PCS Low	PCS High
SBP	mmHg	Decrease from baseline \geq 30 Absolute value <80 mmHg	Increase from baseline \geq 30 Absolute value 121 – 139 Absolute value 140 – 159 Absolute value \geq 160
DBP	mmHg	Decrease from baseline \geq 20 mmHg Absolute value <60 mmHg	Increase from baseline \geq 20 Absolute value 80 – 89

Vital Sign	Unit	PCS Low	PCS High
			Absolute value 90 – 99 Absolute value \geq 100
Pulse	beats per minute	Absolute value \leq 40	Absolute value \geq 120
Respiratory Rate	breaths per minute	Absolute value < 12	Absolute value > 20
Weight	kg	\geq 7% decrease from Baseline	\geq 7% increase from Baseline

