9.2 Exclusion Criteria

Subjects who meet **ANY** of the following criteria are not eligible for this study:

1. Known central nervous system metastases
2. Prior malignancy(s) within the past 3 years, with the exception of curatively treated basal or squamous cell carcinoma of the skin, locally advanced prostate cancer, ductal carcinoma in situ of breast, in situ cervical carcinoma and superficial bladder cancer
3. Prior treatment with panitumumab for subjects with KRAS wt and NRAS wt tumors
4. Known history of keratitis, ulcerative keratitis, or severe dry eye in subjects with KRAS wt and NRAS wt tumors
5. Residual AE from previous treatment > Grade 1, except neuropathy and alopecia
6. Prior intolerance to fluoropyrimidine for subjects with KRAS mut and/or NRAS mut tumors

7. Myocardial infarction within 6 months prior to C1D1, and/or prior diagnoses of congestive heart failure (New York Heart Association Class III or IV), unstable angina, unstable cardiac arrhythmia requiring medication; and/or the subject is at risk for polymorphic ventricular tachycardia (eg, hypokalemia, family history, or long QT syndrome)
8. Uncontrolled hypertension, defined as systolic blood pressure \geq 160 mmHg and/or diastolic blood pressure \geq 100 mmHg confirmed upon repeated measures
9. LVEF $<$ 40% as determined by echocardiogram (ECHO)/multigated acquisition scan (MUGA) performed at screening or within 90 days prior to C1D1
10. QT/QTc interval $>$ 450 msec, as determined by screening ECG performed no earlier than 1 week before C1D1
11. Prior anti-tumor therapy (chemotherapy, radiotherapy, antibody therapy, molecular targeted therapy, retinoid therapy or hormonal therapy) within 4 weeks ($<$ 28 days) prior to C1D1
12. Major surgery within 4 weeks ($<$ 28 days) prior to C1D1
13. Active joint inflammation or history of inflammatory arthritis or other immune disorder involving joints (osteoarthritis is not exclusionary)
14. Active infection involving IV antibiotics within 2 weeks prior to C1D1
15. Known history of or active hepatitis B virus (HBV) and/or hepatitis C virus (HCV), or active tuberculosis
16. Known history of human immunodeficiency virus (HIV) type 1/2 or other immunodeficiency disease
17. Subject has received a live vaccine within 4 weeks ($<$ 28 days) prior to C1D1
18. Known hypersensitivity to any component of recombinant protein production by CHO cells

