8.4 Clinical Laboratory Evaluations

For hematology, chemistry, and coagulation, the observed values and changes from baseline will be summarized. Change from baseline will be calculated as (value at a treatment cycle – value at baseline). Laboratory results will be classified according to the NCI-CTCAE Version 4.03. Grades are assigned based solely on lab values and CTCAE requirements regarding related clinical signs or symptoms are not required.

Therefore, clinical assessment of the subjects could result in a different grade. Laboratory results not corresponding to CTCAE terms will not be graded. Thresholds are specified in Section 16.2. The number (%) of subjects with values that satisfy CTCAE criteria at any time during treatment will be summarized by test, grade, and visit. Each subject will be categorized based on their post-baseline CTCAE grade at each planned assessment time. Shift tables relative to the CTCAE Grade will be used to summarize the change from baseline to the maximum post-baseline CTCAE grade.

A table will summarize the shift in the absence/presence of protein, glucose, and blood in the urine.

Laboratory results will be summarized in standard international units.

Tables summarizing observed values and changes from baseline and shifts in CTCAE grade will be completed for study cohort. The number (%) of subjects with values that satisfy CTCAE criteria at any time during treatment will be provided for the treatment study cohort and integrated treatment group.

All laboratory test results (including urinalysis) will be presented in by-subject data listings. A list of abnormal laboratory values will also be produced where abnormal is defined as a value with CTCAE Grade 1 or higher. If a subject has at least one abnormal value for a specific analyte, all normal and abnormal values for that subject and analyte will be included in the listing.

Post baseline abnormal hepatic and renal results will be summarized by CTCAE Toxicity Grade among subjects with normal results prior to first dose, and a listing will be created to support this table.

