8.5 ECG

12-Lead ECGs will be analyzed for the collected time points. ECG conduction times will include PR interval, QRS duration, QT and QTc interval using Fredericia's correction, and the heart rate. The observed values and changes from baseline will be summarized time points collected. Change from baseline will be calculated as (value at a treatment cycle – value at baseline). Frequencies and percentage of values meeting potentially clinically significant (PCS) criteria ([Table 4](#)) at any time will be presented. The denominator for percentages will be the number of patients who have a value at baseline and post-baseline.

Tables summarizing observed values and changes from baseline will be analyzed. The number (%) of subjects with values that satisfy PCS criteria at any time during treatment will be provided.

All summary tables will be provided for the Part 1 and 2 safety analysis set. All ECG data will be included in a listing.

Table 4: Potentially Clinically Significant Post-baseline ECG Conduction Times

Conduction Time	Unit	PCS Criteria
PR Interval	msec	Absolute value \geq 200
QRS Duration	msec	Absolute value \geq 100
QT Interval	msec	Absolute value \geq 450
QTcF Interval	msec	Males: Absolute Value \geq 450 Females: Absolute Value \geq 470

Conduction Time	Unit	PCS Criteria
	msec	Increase from baseline 30 – 60
	msec	Increase from baseline > 60
Heart Rate	beats per minute	Absolute value \leq 40 Absolute value \geq 120

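### The absolute blood-pressure and ECG lines in the SAP's potentially clinically significant (PCS) tables have no baseline condition, so pre-existing and even improved values count as post-baseline findings

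*SAP*

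**What the plan says.** SAP 8.6 (Vital Signs) reports PCS results as a count of subjects: "The number (%) of subjects with values that satisfy PCS criteria at any time during treatment will be provided for the study cohort". Table 5 lists the systolic PCS High lines as "Absolute value 121 – 139 Absolute value 140 – 159" and then >=160 mmHg. The diastolic lines start at "Absolute value 80 – 89" and continue with 90-99 and >=100 mmHg. None of these lines refers to the subject's own baseline.

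Baseline enters in two other ways. It sets the denominator: "The denominator for percentages will be the number of subjects who have a value at baseline and post-baseline". It also defines separate change rows: 30 mmHg for systolic, 20 mmHg for diastolic, and 7% for weight, which has no absolute line.

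SAP 8.5 (ECG) is built the same way. Table 4 has absolute lines for PR, QRS, QT, QTcF and heart rate, change rows for QTcF only, and the rule "The denominator for percentages will be the number of patients who have a value at baseline and post-baseline".

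On entry, Protocol 9.2 excludes "Uncontrolled hypertension, defined as systolic blood pressure" of 160 mmHg or more and/or diastolic of 100 or more, confirmed on repeat. Screening QT/QTc above 450 msec is also excluded. Systolic 121-159 and diastolic 80-99 are allowed, and no criterion limits PR or QRS.

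For laboratory data, SAP 8.4 does condition on baseline: "Post baseline abnormal hepatic and renal results will be summarized by CTCAE Toxicity Grade among subjects with normal results prior to first dose". It also plans shift tables from baseline to the highest post-baseline CTCAE grade. SAP 8.4.4 does the same kind of thing for urinalysis. SAP 8.5 and 8.6 specify no shift table.

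**The concern.** Both documents define the safety outcome in terms of clinically relevant changes (Protocol 8.4.2.2, SAP 3.2.2). An absolute line with no baseline condition records a state, not a change. Three kinds of subject enter the PCS High counts together: those who newly rise into a band, those who were there before the first dose and stayed, and those who came down into it from a higher band.

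The lowest blood-pressure bands are the most exposed, because they start at ordinary values and the count is taken over repeated readings. If nearly everyone is flagged without any drug effect, the line has little room to show one. Because the bands are separate lines, a real rise can even move subjects out of the 121-139 line and lower its count.

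Blood pressure is a signal worth being able to read here. Protocol 6.4.1 reports a mean rise of about 10% in monkeys, at 200 mg/kg. On an assumed 125 mmHg that is about 12 mmHg (0.10 x 125 = 12.5), well short of the 30 mmHg change row.

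**Working it through.** The SAP states no expected PCS rate, so there is no figure of its own to reproduce.

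**Number of readings.** SAP 16.1 (vital-signs footnote) has vital signs weekly in Cycle 1, then every 2 weeks, before and after imalumab. After baseline, Cycle 1 gives 1 (Day 1 post-dose) + 3 x 2 (Days 8, 15, 22) = 7. Cycle 2 gives 2 x 2 = 4. End of Study and Safety Follow-up add 2. The total over two cycles is 13. A control on best supportive care, with one reading per visit, has 3 + 2 + 2 = 7.

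**One subject, by hand.** Take a true systolic mean of 115 and a within-subject SD of 8 (assumed), with no drug effect.
- Chance that one reading falls in 121-139: p = Φ((139.5 − 115)/8) − Φ((120.5 − 115)/8) = 0.9989 − 0.7541 = 0.245.
- Chance of at least one in 13: 1 − (1 − 0.245)^13 = 0.97.

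**Population model (assumed, because the documents give no distributions).** Reading = subject mean + noise, no drug effect, 200,000 simulated subjects per scenario, baseline kept only if systolic <160 and diastolic <100. Mean / between-subject SD / within-subject SD:
- Systolic: 115/11/7 (low), 125/13/8 (mid), 132/14/10 (high).
- Diastolic: 70/7/5, 75/8/6, 78/9/7.

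Subjects flagged at any time, 13 readings:

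| Line | Low | Mid | High |
|---|---|---|---|
| SBP 121-139 | 70% | 89% | 94% |
| SBP 140-159 | 14% | 46% | 71% |
| SBP >=160 | 0.2% | 5% | 20% |
| DBP 80-89 | 44% | 73% | 84% |
| DBP 90-99 | 7% | 30% | 49% |
| DBP >=100 | 0.3% | 4.5% | 14% |
| Baseline SBP already >=121 | 34% | 61% | 73% |
| An SBP High reading in a band below the baseline band | 3% | 15% | 27% |

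**ECG, five recordings (assumed), low / mid / high.** The second set of figures is the share of all subjects who are flagged and did not meet the line at baseline. Inputs were PR 155/18/7, 160/22/8, 168/24/10; QRS 88/9/4, 92/10/5, 96/12/5; QT 405/18/8, 412/20/10, 420/20/12, with entry QT <=450.
- PR >=200: 2 / 9 / 21%, of which new 2 / 5 / 11%.
- QRS >=100: 22 / 42 / 56%, of which new 12 / 20 / 19%.
- QT >=450: 2 / 7 / 16%, all new because entry already limits it.

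Pulse and respiratory-rate lines flag about 1-8% each.

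**Effect of a true +12 mmHg shift, 13 readings.** The SBP 121-139 line goes from 70/89/94% to 92/87/82%, so in the mid and high scenarios a harmful shift lowers it. The 30 mmHg increase row picks up only 23/33/49%.

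**Effect of a baseline-referenced rule.** Count a subject if the worst post-baseline systolic band is worse than the baseline band. With no drug effect this gives 47/60/72%, against 70/90/97% for any systolic High line. In the mid scenario a +12 mmHg shift moves any systolic High from 90% to 98% (8 points) and the worse-band count from 60% to 92% (32 points).

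**Effect of unequal reading counts.** With no drug effect, 13 against 7 readings changes the SBP 140-159 line from 10/39/63% to 14/46/71%, a gap of about 3/7/8 points.

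**The case against.** The case for leaving the tables alone has several sound parts.

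- **Baseline is not ignored.** Tables 4 and 5 have change rows, weight is judged only by change, and changes from baseline are summarised by time point. Abnormal vital signs are also assessed for adverse event reporting (Protocol 12.8), and treatment-emergent events are tabulated by CTCAE grade (SAP 8.3). A reader might infer that the PCS tables are the only categorical safety output for these measures; they are not.
- **A shift table may already be promised.** The paragraph on ECG, vital signs and laboratory values in Protocol 13.4.4.2 ends with shift tables of new or worsening findings. Its scope is ambiguous, and SAP 5.5 does not list it as dropped.
- **Flagging of most subjects is not general.** It holds for the lowest systolic band, and for the lowest diastolic band in the mid and high scenarios. Systolic 140-159 and QRS pass half only in the high scenario. Entry limits systolic >=160, diastolic >=100 and QT/QTc, so those lines are largely new by design.
- **The tables are descriptive.** No test, stopping rule or endpoint uses them, and the SoC cohorts show a background rate under the same rule. Systolic 140-159 does respond to a real effect, so it would be wrong to say the tables cannot separate an effect from none.
- **The reading imbalance is limited.** Protocol Tables 4 and 5 require pre-dose and post-dose readings during SoC treatment as well. A control on an every-2-week regimen (assumed) has about 11 readings against 13, a gap of about 2 points on the 140-159 line at mean 125. A gap of 8 points or so would need every control to be on best supportive care, a share the documents do not give.
- **SAP 8.4 is only a partial precedent.** The hepatic and renal table is conditioned on baseline, but the same section also counts CTCAE abnormalities at any time with no such condition.

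What remains is the construction of the absolute lines. None of these points stops an unchanged or improved subject being counted under PCS High, and the 30 mmHg row is too coarse to replace the bands.

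**Conclusion.** The absolute PCS lines in SAP 8.5 and 8.6 mix pre-existing, improved and new values. That follows from the text and needs no assumption. The size does need assumptions: with no drug effect and 13 readings, about 70-94% of subjects are flagged for systolic 121-139 and 44-84% for diastolic 80-89, and 3-27% have a systolic High reading in a band below their baseline band. The direction is stable across the scenarios; the percentages are not, and should be quoted only with the assumed distributions.

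It would go too far to conclude that the vital-sign and ECG tables as a whole flag most subjects, or that they are biased between arms by a known amount. This is a cheap improvement to descriptive safety tables and does not affect the primary analysis.

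**What to change.** In SAP 8.6, for blood pressure, place each subject once in the worst post-baseline band and tabulate baseline band against worst post-baseline band. Count as treatment-emergent only subjects whose worst band is worse than baseline. Keep everyone with a baseline and a post-baseline value in the denominator. This matches the shift tables in SAP 8.4 and settles the ambiguity in Protocol 13.4.4.2. Restricting the denominator to subjects not yet in a High band is not advised for blood pressure. It would remove about 34/61/73% of subjects and leave about 15, 9 or 6 of the roughly 22 per imalumab cohort in SAP 2.3 (22 x 0.66, 0.39, 0.27).

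In SAP 8.5, report the absolute PR, QRS, QT and QTcF lines among subjects not meeting the criterion at baseline.

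For the columns that set arms side by side, use scheduled pre-dose or visit readings, because best-supportive-care controls have no post-dose reading.

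Cost: SAP wording and a little more programming, with no new data. ECG denominators become smaller. Transient post-dose changes drop out of the between-arm columns, but stay in the overall table and the listings. A sizeable background remains, about 47-72% with a worse systolic band under no effect, because of the low 121 mmHg cut-off and the repeated readings.

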10.3.3 Treatment Cycles

After all baseline assessments have been completed, subjects will begin treatment Cycle 1 with administration of their first dose of imalumab. Subjects will receive imalumab QW on Days 1, 8, 15, and 22 as part of a 4-week/28-day treatment cycle. A new cycle should begin after every 28-day period (ie, 4 weeks). For all subjects, treatment will continue until disease progression, unacceptable toxicity, withdrawal of consent, or for any other reason as detailed in Section [9.3](#).

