10.3.3.3 Day 8 of Each Cycle

On Day 8 of each treatment cycle in both Parts 1 and 2 of the study (unless otherwise depicted below), the following assessments/treatment administrations will occur:

Prior to administration of study drug:

- Vital signs (including body temperature, heart rate, blood pressure, respiratory rate, and weight; recorded within 30 minutes prior to start of treatment)
- Clinical laboratory assessments:
 - Cycle 1 only: hematology, serum chemistry, and coagulation
 - All subsequent cycles: hematology
- Collection of AEs
- Review of concomitant medications/ non-drug therapies
- Entry into IRT System (Part 1: all subject visits; Part 2: Arm A subject visits only)
- On Day 8 of Cycle 1 only:
 - For subjects receiving imalumab treatment, blood samples for PK (imalumab plasma levels) and PD biomarkers (oxMIF and total MIF) are collected **-2 to 0 h predose** (see [Table 6](#)).

Administration of study treatment(s):

- Imalumab administration:
 - Part 1: all subjects
 - Part 2: subjects in Arm A
- SoC administration (if applicable):
 - Part 2, Arm B: For SoC, drug dose and schedule to be given in accordance with product label.

Following administration of study treatment:

- Vital signs measurement should be recorded within 30 minutes of completion of the imalumab injection
- On Day 8 of Cycle 1 only:
 - For subjects receiving imalumab treatment, blood samples for PK (imalumab plasma levels) and PD biomarkers (oxMIF and total MIF) are collected **0 to 2 h postdose** (see [Table 6](#)).

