^e Vital signs, including body temperature, heart rate, blood pressure, and respiratory rate, are to be measured after a 5-minute rest. Sitting position is recommended for blood pressure measurement. Height and body weight will also be recorded. On the day of imalumab administration, vital signs will be taken within 30 minutes prior to dosing and within 30 minutes after completion of imalumab infusion. Weekly monitoring to be done in Cycle 1 only, then Q2W.

Continued on next page

Continued

- ^f The 12-lead ECG assessment at Screening should be performed no earlier than 1 week before C1D1. The 12-lead ECG assessment should be performed predose and 2 (\pm 1) hours postdose on Day 1 (Baseline, C1D1).
- ^g Laboratory assessments should be evaluated before drug administration. Immediately prior to Cycle 1, laboratory assessments can be performed either on Day -1 or on Day 1 predose. Hematology tests will be done weekly during each treatment cycle. Chemistry/coagulation tests will be done on Day 1 and Day 15 of each treatment cycle, and Day 8 of Cycle 1 only. Laboratory tests include hematology (complete blood count with differential and platelet counts) and biochemistry (creatinine, creatinine clearance according to Cockcroft-Gault, sodium, potassium, calcium, magnesium, glucose, albumin, alanine aminotransferase, aspartate aminotransferase, alkaline phosphatase, total bilirubin, C-reactive protein, and blood urea nitrogen). Coagulation panel includes International Normalized Ratio and activated partial thromboplastin time.
- ^h Serum human chorionic gonadotropin to be tested at screening; urine dipstick test to be performed on Day 1 of each cycle (prior to dosing), End of Study/Early Termination Visit, and at Safety Follow-up. A serum pregnancy test will be performed to confirm if a positive result is obtained in a dipstick test.
- ⁱ If not readily available, genetic testing for KRAS/NRAS mutation status needs to be done early enough to allow randomization within 4 weeks. If KRAS mutation status is known, the subject can start treatment while NRAS testing is pending.
- ^j Baseline CT or MRI scans can be accepted within 28 days prior to first imalumab administration (C1D1); assessments are to be repeated every 2 cycles using the same method at each measurement and tumor response evaluated before starting the next cycle. A 7-day window is permitted for all imaging studies for tumor measurement purposes.

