Table 4 Schedule of Study Procedures and Assessments: SoC Following Randomization (4-Week Cycles or if Subject is on Best Supportive Care)								
Trial Periods	Screening Visit	Baseline Visit	Study Visits Per Treatment Cycle ^a				End of Study/ Early Termination Visit	Safety Follow-Up Visit ^b
Study Days	Days -28 to -1	Day 1 Predose	Days 1 to 7	Days 8 to 14	Days 15 to 21	Days 22 to 28		
Treatment Schedule								
EORTC QLQ-C30		X					X	X
EORTC QLQ-CR29		X					X	X
EQ-5D		X					X	X
12-lead ECG ^f	X	X	Day 1				X	X
ECHO/MUGA	X							
Hematology ^g	X	X	Day 1	Day 8	Day 15	Day 22	X	X
Chemistry/coagulation ^g	X	X	Day 1	Day 8 (Cycle 1 only)	Day 15		X	X
Pregnancy test ^h (if applicable)	X	X	Day 1				X	X
Urinalysis	X	X	Day 1				X	X
Genetic testing ⁱ (KRAS/NRAS)	X							
Tumor measurement (RECIST v1.1) ^j	X					Day 28 of Cycle 2 and then every other cycle	X ^k	X ^k
Adverse Event ^l	X	X	X	X	X	X	X	X

Table 4 Schedule of Study Procedures and Assessments: SoC Following Randomization (4-Week Cycles or if Subject is on Best Supportive Care)									
Trial Periods		Screening Visit	Baseline Visit	Study Visits Per Treatment Cycle^a				End of Study/ Early Termination Visit	Safety Follow-Up Visit^b
Study Days	Procedures/Assessments	Days -28 to -1	Day 1 Predose	Days 1 to 7	Days 8 to 14	Days 15 to 21	Days 22 to 28		
Treatment Schedule									
Concomitant medications/non-drug therapies		X	X	X	X	X	X	X	X

Abbreviations: AE=adverse events; C1D1=Cycle 1 Day 1; cfDNA=cell-free DNA; CT=computerized tomography; ECG=electrocardiogram; ECHO=echocardiogram; ECOG PS=Eastern Cooperative Oncology Group Performance Status; EORTC QLQ-C30=European Organization for Research and Treatment of Cancer Quality of Life Questionnaire Core 30; EORTC QLQ-CR29=European Organization for Research and Treatment of Cancer Quality of Life Questionnaire for colorectal cancer 29; EQ-5D=European Quality of Life – 5 Dimensions; IRT=Interactive Response Technology; MRI=magnetic resonance imaging; MUGA=multigated acquisition scan; Q2W=every 2 weeks; RECIST=Response Evaluation Criteria in Solid Tumors; SoC=standard of care.

^a Treatment cycles for SoC are defined in this study as 3-week or 4-week cycles. Treatment cycles will continue until progression, unacceptable toxicities, or withdrawal of consent.

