^b The Safety Follow-up Visit should occur 30 (± 7) days after the last dose of study treatment. For subjects who have stopped study drug or have documented disease progression, post-study telephone calls to assess overall survival will be made by site staff every 3 months.

^c Subject informed consent occurs at screening, prior to any study-specific procedure.

^d IRT will be utilized at screening and baseline visits only for all subjects randomized to Arm B (Part 2) to receive SoC/best supportive care.

^e Vital signs, including body temperature, heart rate, blood pressure, and respiratory rate, are to be measured after a 5-minute rest. Sitting position is recommended for blood pressure measurement. Height and body weight will also be recorded. Weekly monitoring to be done in Cycle 1 only, then Q2W. Vital signs should be evaluated both predose and postdose during treatment with SoC.

^f The 12-lead ECG assessment should be performed predose and 2 (± 1) hours postdose on Day 1 (Baseline, C1D1).

Continued on Next Page

Continued

- ^g Laboratory assessments should be evaluated before drug administration. Immediately prior to Cycle 1, laboratory assessments can be performed either on Day -1 or on Day 1 predose. Hematology tests will be done weekly during each treatment cycle. Chemistry/coagulation tests will be done on Day 1 and Day 15 of each treatment cycle, and Day 8 of Cycle 1 only. Laboratory tests include hematology (complete blood count with differential and platelet counts) and biochemistry (creatinine, creatinine clearance according to Cockcroft-Gault, sodium, potassium, calcium, magnesium, glucose, albumin, alanine aminotransferase, aspartate aminotransferase, alkaline phosphatase, total bilirubin, C-reactive protein, and blood urea nitrogen). Coagulation panel includes International Normalized Ratio and activated partial thromboplastin time.
- ^h Urine dipstick test to be performed on Day 1 of each cycle (prior to dosing), End of Study/Early Termination Visit, and at Safety Follow-up. A serum pregnancy test will be performed to confirm if a positive result is obtained in a dipstick test.
- ⁱ If not readily available, genetic testing for KRAS/NRAS mutation status needs to be done early enough to allow randomization within 4 weeks. If KRAS mutation status is known, the subject can start treatment while NRAS testing is pending.

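### The any-time vital-sign abnormality count in SAP 8.6 can run higher in Arm A than in SoC with no drug effect, because the number of readings and the time on treatment can differ by arm

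*SAP*

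**What the plan says.** **The counting rule.** SAP 8.6 states: "The number (%) of subjects with values that satisfy PCS criteria at any time during treatment will be provided for the study cohort", and also for the integrated treatment group. SAP Table 1 lists imalumab and SoC groups under both. The denominator is fixed by subject: "The denominator for percentages will be the number of subjects who have a value at baseline and post-baseline". The section does not say which readings enter the count, and it makes no allowance for their number or for time on treatment. It also summarises observed values and changes by collected time point and lists all readings. It plans no test of PCS rates.

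**Arm A schedule.** Protocol 10.3.3: "Subjects will receive imalumab QW on Days 1, 8, 15, and 22 as part of a 4-week/28-day treatment cycle". On imalumab days, footnote e of Protocol Table 3 says "vital signs will be taken within 30 minutes prior to dosing and within 30 minutes after completion of imalumab infusion". The visit text agrees; for Day 8 of each cycle it says "Vital signs measurement should be recorded within 30 minutes of completion of the imalumab injection", with equivalent instructions for Days 1, 15 and 22.

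**Control schedule.** Footnote e of Protocol Tables 4 and 5 says "Vital signs should be evaluated both predose and postdose during treatment with SoC". Table 4 also covers controls who receive no drug, as its title shows: "SoC Following Randomization (4-Week Cycles or if Subject is on Best Supportive Care". The visit text names a post-treatment reading only after imalumab.

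**Frequency after Cycle 1.** Footnote e in Tables 3, 4 and 5 says "Weekly monitoring to be done in Cycle 1 only, then Q2W". The visit text for Day 8 and Day 22 asks for vital signs in every cycle. These instructions conflict.

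**The concern.** A flag that is set by any one abnormal reading becomes more likely with each extra reading, even when the risk per reading is the same. Two features can give Arm A more readings: the second reading on imalumab days, and longer treatment if the planned PFS difference appears. A reader comparing PCS percentages by eye, with a planned 22 controls, could take a difference in measurement for a drug effect. The extra Arm A readings also fall within 30 minutes of an infusion. A control on best supportive care has no such reading.

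Safety and tolerability is a secondary objective and vital signs are a named safety outcome, so the table will be read. It does not touch PFS or the sample size.

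**Working it through.** The documents give no PCS rate or reading count, so there is no figure of theirs to reproduce.

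**Inputs from the documents.** Imalumab is given on 4 days per 28-day cycle. Arm A has 2 readings per imalumab day. Controls have 1 reading per visit, plus 1 on SoC dosing days under Tables 4 and 5. SAP 5.3 takes the last assessment before first dose as baseline, so one reading is removed in each arm.

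**Inputs assumed.** Per-reading PCS probability p = 0.02, 0.05 or 0.10, equal in both arms. Within-subject correlation ρ from 0 to 0.5.

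**Step 1: post-baseline readings over 8 weeks (two 28-day cycles).**

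- (a) Visit text for both arms: Arm A 2 × 8 − 1 = 15; control 8 − 1 = 7. The same 7 applies to best supportive care on weekly visits under Table 4.
- (b) Footnote e for both arms, best supportive care: Arm A (2 × 4 − 1) + 2 × 2 = 11; control (4 − 1) + 2 = 5.
- (c) Footnote e for both arms, SoC every 2 weeks: Arm A 11; control (4 + 2 − 1) + (2 + 2) = 9.
- (d) Weekly visits, SoC dosed weekly with pre- and post-dose readings: 15 and 15.
- (e) Arm A on the imalumab-day rule throughout, best supportive care dropping to every 2 weeks after Cycle 1: 15 and 5.
- (f) Weekly visits in both arms, SoC every 2 weeks with pre- and post-dose readings: 15 and 8 + 4 − 1 = 11.

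**Step 2: chance of at least one PCS reading in m readings.** For independent readings this is 1 − (1 − p)^m. For correlated readings a beta-binomial is used, with a = p(1/ρ − 1) and b = (1 − p)(1/ρ − 1). Example for (a), p = 0.05, ρ = 0: Arm A 1 − 0.95^15 = 53.7%; control 1 − 0.95^7 = 30.2%; ratio 1.78.

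| Case | Readings, A vs control | p = 0.05, ρ = 0 | Ratio | p = 0.05, ρ = 0.5 ratio | Ratio over all p and ρ |
|---|---|---|---|---|---|
| (a) | 15 vs 7 | 53.7% vs 30.2% | 1.78 | 1.25 | 1.23-1.98 |
| (b) | 11 vs 5 | 43.1% vs 22.6% | 1.91 | 1.29 | 1.27-2.07 |
| (c) | 11 vs 9 | 43.1% vs 37.0% | 1.17 | 1.06 | 1.06-1.20 |
| (d) | 15 vs 15 | 53.7% vs 53.7% | 1.00 | 1.00 | 1.00 |
| (e) | 15 vs 5 | 53.7% vs 22.6% | 2.37 | 1.41 | 1.37-2.72 |
| (f) | 15 vs 11 | 53.7% vs 43.1% | 1.24 | 1.09 | 1.08-1.31 |

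At p = 0.05 and ρ = 0.1, cases (a) and (f) give 37% in Arm A, against 24% on best supportive care and 32% on SoC every 2 weeks.

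**Step 3: time on treatment.** Planned median PFS is used as a stand-in for time on treatment. 2.4 months × 365.25/12/7 = 10.4 weeks; 4.25 months gives 18.5 weeks. With one reading per week in both arms, p = 0.05 and ρ = 0: 1 − 0.95^10 = 40.1% for control and 1 − 0.95^18 = 60.3% for Arm A. At ρ = 0.1 the figures are 30% and 41%. This gap arises with identical visit schedules, so matching predose readings alone does not remove it.

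**Step 4: check of the remedy.** With only the shared weekly predose reading over the same 8 weeks, m = 7 in each arm. The rates are then 13.2%, 30.2% and 52.2% in both arms for p = 0.02, 0.05 and 0.10 (ρ = 0), ratio 1.00. If both arms drop to every 2 weeks after Cycle 1, m = 5 in each and the ratio is again 1.00.

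**The case against.** The strongest reply is that the doubling of readings is not peculiar to Arm A. Tables 4 and 5 ask for pre- and post-dose readings during SoC, and the visit text allows SoC dosing on Days 8, 15 and 22. For actively dosed controls the gap is small (case c) or nil (case d). This stands. A reader might infer that the Arm A rate is certainly inflated, or that controls in general are read half as often. The documents support neither: both would require knowing the SoC mix and which schedule sites follow.

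Second, the mild bands (SBP 121-139, DBP 80-89) may be crossed so often that both arms saturate. At an assumed 30% per reading and ρ = 0, 15 versus 7 readings give 99.5% versus 91.8%, a ratio of only 1.08. This also stands: the effect is largest for uncommon abnormalities, so reading count need not drive every row. Weight is taken once per visit, before dosing (Protocol 12.8), so pre/post doubling does not affect its row, although longer follow-up does.

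Third, a reader might infer that infusion-related change is hidden. That goes too far. SAP 8.6 also summarises by collected time point, all readings are listed, and infusion reactions are a separate outcome in SAP 3.3.

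Fourth, the table is descriptive, and a bias that makes imalumab look worse would not conceal a safety signal. That limits the priority. It does not make the any-time percentages comparable. None of the schedules examined gives Arm A fewer readings than control, so the distortion is not balanced.

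**Conclusion.** The point holds as a limited one. Because SAP 8.6 counts any reading during treatment, the Arm A rate for PCS blood pressure, pulse and respiratory rate can exceed the SoC rate with no drug effect. Under the assumed 2-10% per-reading risk and correlation 0-0.5, over 8 weeks:

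- 1.0 if SoC is dosed weekly with pre- and post-dose readings;
- about 1.06-1.20 for SoC every 2 weeks under footnote e;
- about 1.2-2.1 against best supportive care when both arms follow the same source for visit frequency;
- up to about 2.7 if Arm A follows the imalumab-day rule while best supportive care drops to every 2 weeks.

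Longer Arm A treatment would add to this if the planned PFS difference is realised. The per-reading risks and correlations are assumptions, and the documents do not give the SoC mix. They therefore support saying that inflation is possible, not that it will occur or how large it will be. Low priority: no test or decision rests on the table.

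**What to change.** In SAP 8.6:

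1. Base the Arm A versus SoC PCS comparison on scheduled predose (or single-visit) readings within a common time window, for example the first 8 weeks. Alternatively, report PCS readings per reading taken.
2. Keep the all-readings any-time table by cohort, labelled as a within-cohort safety summary.
3. Show post-infusion or post-dose readings separately, as change from the same-day predose value.
4. Keep all readings in the listings.

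In the protocol, reconcile footnote e of Tables 3 to 5 with the imalumab-day rule in the same Table 3 footnote and with the visit text for Day 8 and Day 22 of each cycle. Reconcile the post-dose reading for SoC in Tables 4 and 5 with the visit text, which names one only after imalumab. The SAP should then state which scheduled readings enter each table.

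The cost is SAP wording, one extra descriptive table and the protocol clarification, with no new data. The between-arm comparison will rest on fewer readings. A fixed window also does not fully equalise follow-up if subjects leave treatment before it ends, so the number of readings per cohort should be shown beside the percentages.
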